In PARADIGM-HF (the ‘Prospective Comparison of ARNI [Angiotensin Receptor Neprilysin Inhibitor] with ACEI [Angiotensin-Converting–Enzyme Inhibitor] to Determine Impact on Global Mortality and Morbidity in Heart Failure Trial’), a large pivotal phase III outcome trial in more than 8,400 HF patients with NYHA class II-IV and an ejection fraction $\leq 40\%$, LCZ696 significantly reduced the composite endpoint of cardiovascular mortality and the risk of hospitalization. It also significantly decreased the symptoms and physical limitations associated with HF compared with the ACEI enalapril. The LCZ696 group had higher proportions of patients with hypotension and non-serious angioedema but lower proportions with renal impairment, hyperkalemia, and cough than the enalapril group ([McMurray et al 2014](#)).

LCZ696 has been approved in 2015 in the United States (US), the European Union (EU), and in various other countries (e.g. Chile, Saudi-Arabia, Switzerland, Kuwait, Taiwan, Argentina, Canada, Israel, Australia, Singapore).

Based on the observation that sacubitril inhibits the organic anion-transporting polypeptides OATP1B1 and OATP1B3 *in vitro* Novartis conducted a drug-drug interaction (DDI) study with the HMG-CoA reductase inhibitor atorvastatin ([Pan et al 2013 – CLCZ696B2115 Full Study Report](#)) in which LCZ696 increased the maximal plasma concentrations (c_{max}) of the OATP1B1 and OATP1B3 substrates atorvastatin and its metabolites by up to 2-fold. However, the areas under the curve (AUCs) of atorvastatin and its metabolites were not increased to a clinically significant extent (<1.3 -fold), suggesting that the impact of sacubitril on the pharmacokinetics of atorvastatin is limited to c_{max} , potentially due to the short half-life of sacubitril (~1.5 h). Indeed, sacubitril is rapidly absorbed and rapidly metabolized to form LBQ657 and does not result in a DDI with valsartan, another OATP1B1/1B3 substrate. Furthermore, no significant increase in potential statin-related adverse events was observed in PARADIGM-HF, wherein patients were co-administered with LCZ696 200 mg bid and any statin (N=2,369).

Therefore, the EU SmPC recommends “that caution should be exercised when co-administering Entresto with statins”.

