Population-based NIS vary considerably with respect to the reported incidence of myopathy which may be highly dependent on the frequency of CK measurement. Van Staa et al (2014) reported that only 20% of patients have a CK measurement recorded in the United Kingdom (UK) based Clinical Practice Research Datalink (CPRD). A study that used data from two different primary care databases in the UK (i.e. ‘The Health Improvement Network’ [THIN] and ‘IMS MediPlus’) reported a 10-fold difference in the incidence of myopathy in statin users (Molokhia et al 2008).

In a cohort study using primary care information from the UK, Gaist et al (2001) found an incidence rate (IR) of myopathy in association with current statin use of 1.2/10,000 person-years (PYs). Cziraky et al (2006) reported an IR of 1.6-3.5/10,000 PYs for statin monotherapy-associated myopathy requiring hospitalization (including rhabdomyolysis)

based on US administrative health claims data. [McClure et al \(2007\)](#) estimated – in a cohort of patients with CK monitoring in a managed care organization population from the US – an IR of 9.1/10,000 PYs for myositis in statin-exposed patients without liver or renal disease and without concomitant fibrate exposure and an IR of 639/10,000 PYs in statin-treated patients with liver and renal disease and with concomitant fibrate use. The corresponding IR estimates in a cohort without CK monitoring from the same study was markedly lower (i.e. 2.2 and 593/10,000 PYs, respectively). [Molokhia et al \(2008\)](#) estimated an annual incidence of statin-induced myopathy or myalgia of 6.9/10,000 population based on data from THIN, a UK primary care database. [Smeeth et al \(2009\)](#) report a cumulative incidence for any diagnosed muscle problems of 4.1/10,000 in the first year of statin treatment. [Hippisley-Cox and Coupland \(2010\)](#) estimated an IR for moderate or serious myopathy of approximately 1-2/10,000 PYs in another population-based study in primary care patients from England and Wales. [Nichols and Koro \(2007\)](#) report ‘prevalence rates’ in statin initiators (without diabetes) of 268/10,000 PYs for any myopathic event, 67/10,000 PYs for myalgia, 45/10,000 PYs for mild myositis (with normal CK), and 8/10,000 PYs for severe myositis (CK 4-10 x upper limit of normal [ULN]).

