7.3.2 Outcomes of interest

Outcomes of interest will be identified using the event-specific codes based on the coding system(s) used in the database(s) of interest (e.g. READ, International Classification of Diseases, 9th or 10th revision [ICD-9, or ICD-10], International Classification of Primary Care [ICPC]). Laboratory values will in general only be used to verify the certainty of a diagnosis, which may be used in sensitivity analyses (e.g. any case, laboratory confirmed cases only). Cases will not be identified based on using laboratory data alone to avoid inclusion of asymptomatic cases that were coincidentally detected because of screening that happened for other purposes.

Suggested terms that will be included in the mapping are listed in Annex 3 [Section 12.3.2](#). Narrative searches for identification of cases will be limited to PHARMO as free text does not add value or is absent/unavailable in the other databases.

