7.3.2.1 Myotoxicity

Myotoxicity is defined as myalgia (muscle pain without evidence of raised CK), myositis (muscle symptoms with raised CK, typically < 10-times ULN), rhabdomyolysis (muscle symptoms with markedly raised CK, typically > 10-times ULN). Since not all of the database may systematically record all CK levels, we will not look at asymptomatic CK increases. These conditions will be identified using event-specific codes and laboratory measurements where available. Based on the publication by [Wiley et al \(2015\)](#), which made a systematic assessment of different phenotyping algorithms using US electronic medical record (EMR) data, the best performance is a combined approach of codes, laboratory measurements and textual searches. However, this may not be possible in all databases or applicable to EU data. Database specific algorithms will be developed. [Table 7-2](#) shows the components that may be used for each of the databases.

For individual terms to identify cases with myotoxicity, see [Annex 12.3.2.1](#).

Validation will be performed for all potential cases in the databases that allow for this and have not yet validated these outcomes before. We will also assess the number of potentially

missed cases that were asymptomatic but had raised CK levels, to assess the potential impact on the study results.

Table 7-2 Components for the identification of myotoxicity by database

	Database (country)				
	PHARMO (NL)	HSD (IT)	Aarhus (DK)	CPRD (UK)	SIDIAP (ES)
Codes	ICPC/ICD-10	ICD-9	ICD-10	READ	ICD-9/10
Laboratory (CK)	Yes	Yes	Yes	Yes	Yes
Text / symptoms	Yes	No	No	No	No

CK = creatine kinase; CPRD = Clinical Practice Research Datalink; DK = Denmark; ES = Spain; HSD = Health Search CSD Longitudinal Patient Database; ICD = International Classification of Diseases; ICPC = International Classification of Primary Care; IT = Italy; NL = the Netherlands; SIDIAP = Sistema d'Informació per al Desenvolupament de la Investigació en Atenció Primària; UK = United Kingdom

Note: details on databases, see [Section 7.4](#)

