7.9 Limitations of the research methods

The limitations of this study will be mainly due to the availability and level of detail of data. Not all potential confounders (e.g. life style factors such as smoking and alcohol use; or body mass index [BMI] which is a very dynamic variable and which is not well recorded or not recorded at all) are contained in (all) databases, this may lead to residual confounding.

Information on the prescribed dose and duration of a prescription is not contained in all databases and has to be estimated, which might lead to some misclassification of exposure, however, we do capture recency of exposure and can explore the effects of dose in PHARMO and CPRD which will allow us to assess the extent of this effect. Since LCZ696 may be prescribed by specialists initially we may misclassify exposure if it is not recorded in the databases. This would attenuate an effect since it is likely to be non-differential; a sensitivity analysis will be planned to address this.

All of the databases, apart from the Aarhus University Prescription Database and PHARMO, have information on prescription only and not on dispensing. None has information on actual drug intake. This implies that we do not know whether the patient actually took the drug – however, this may be non-differential leading to underestimation of risk.

Misclassification of endpoints as well as confounders is possible. For the different databases that will be used, validation studies have shown that coding is reliable in the databases and that these databases are suitable for pharmacoepidemiological research. For those databases where free text is available (PHARMO, HSD, CPRD and SIDIAP), validation of endpoints will be conducted and comparison of incidence rates of endpoints among databases in the quality run will allow checking for internal and external validity. Laboratory measurements will be needed for case finding/validation and the availability of these data will vary across the databases. The amount of misclassification of the outcome may differ between databases due to differences in availability of validation data or laboratory confirmations. However, since cases and controls are sampled and analyzed within the same database, misclassification will be similar for matched cases and controls in the same database. Bias due to misclassification of the outcomes may just differ between the databases.

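### Section 7.9 judges outcome misclassification by comparing cases with controls, when the comparison that matters is detection in LCZ696 users versus non-users; nothing listed in the protocol checks that

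*Protocol*

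**What the plan says.** Section 7.9 accepts that endpoints may be misclassified and that the extent may vary by database. It then argues that, because sampling and analysis stay within a database, "misclassification will be similar for matched cases and controls in the same database", and closes with "Bias due to misclassification of the outcomes may just differ between the databases".

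On laboratory data, the protocol makes these statements:
- Section 7.3.2: "Laboratory values will in general only be used to verify the certainty of a diagnosis, which may be used in sensitivity analyses". It adds: "Cases will not be identified based on using laboratory data alone to avoid inclusion of asymptomatic cases".
- Section 7.3.2.1, on myotoxicity: "These conditions will be identified using event-specific codes and laboratory measurements where available". Myalgia counts without raised CK, while myositis and rhabdomyolysis are defined with raised CK. Potentially missed asymptomatic patients with raised CK will be counted, but no split by LCZ696 use is mentioned.
- Section 7.9: "Laboratory measurements will be needed for case finding/validation and the availability of these data will vary across the databases".
- Section 7.7.2 bases the final analysis on validated cases.

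Section 5 says of the reported incidence of myopathy: "which may be highly dependent on the frequency of CK measurement". It also cites the EU label: "that caution should be exercised when co-administering Entresto with statins".

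The covariates in Sections 7.3.3.1 to 7.3.3.4 contain no count of CK tests, liver tests or visits. The nearest proxies are the numbers of statin prescriptions and of different ATC codes in the prior year. Section 7.7.2.5 leaves to the SAP the sensitivity analyses directed at the limitations, and names only missing first prescriptions of LCZ696.

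**The concern.** Misclassification that is alike in cases and controls is the condition one wants for exposure. For the outcome, the condition is that the chance of being recorded as a case does not depend on exposure. Drawing both groups from one database, and matching on age, sex and index date (Section 7.2.2.4.1), leaves that chance free to differ between LCZ696 users and non-users.

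The protocol contains the elements of such a difference. Recorded incidence varies with how often CK is measured, and the label draws prescribers' attention to exactly the combination under study. If LCZ696 users are tested more, more of their events receive a code, and the OR rises with no true interaction. The study could then fail to rule out its margins or report a false signal.

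Because Section 7.7.2.5 ties sensitivity analyses to the limitations and Section 7.9 does not recognise this one, nothing in the protocol directs anyone to look for it.

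**Working it through.** **Baseline.** The protocol gives no figure for this bias. Its sample size is the reference point. With true OR 1, four controls per case, exposure p = 0.20 in controls, one-sided 5% and 80% power:

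n = (1.645 + 0.842)² × [1/(p(1−p)) + 1/(4p(1−p))] / (ln margin)²

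This gives 40.02 cases for margin 3 and 18.65 for margin 5, against 40 and 19 in Section 7.5. Table 7-6 is reproduced and not in dispute. It assumes equal detection in both exposure groups.

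**Bias formula.** With no true effect, expected OR = r = detected rate in LCZ696 users / detected rate in non-users. If a share t of a group is tested, detected rate = t × (rate with CK monitoring) + (1 − t) × (rate without).

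**Inputs from Section 5.**
- 20% of UK CPRD patients have a CK measurement; this is taken as t in non-users.
- One US study gives myositis rates per 10,000 PYs with and without CK monitoring: 9.1 and 2.2 (no liver or renal disease, no fibrate), and 639 and 593 (liver and renal disease plus fibrate).
- A cohort of statin initiators gives 67 for myalgia, 45 for mild myositis with normal CK and 8 for severe myositis with raised CK, per 10,000 PYs.

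The share of LCZ696 users tested is not in the protocol. It is an assumption, shown as a range.

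**Detected rates at t = 20%, 40%, 60%, 100%.**
- First pair: 3.58, 4.96, 6.34, 9.10.
- Second pair: 602.2, 611.4, 620.6, 639.
- Third approach: only the raised-CK component scales, by the first pair's ratio r, so OR = (67 + 45 + 8r)/120.

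| LCZ696 users tested | 9.1 vs 2.2 | 639 vs 593 | Only raised-CK myositis scales |
|---|---|---|---|
| 20% | 1.00 | 1.00 | 1.00 |
| 40% | 1.39 | 1.02 | 1.03 |
| 60% | 1.77 | 1.03 | 1.05 |
| 100% | 2.54 | 1.06 | 1.10 |

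A further check: if half of cases are recorded whatever the testing and half only when tested, 40% against 20% gives (0.5 + 0.5 × 0.4)/(0.5 + 0.5 × 0.2) = 0.70/0.60 = 1.17.

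**Consequence for the tests.** Exposure in cases is p1 = r·p/(1 − p + r·p), and SE² = 1/(n·p1(1−p1)) + 1/(4n·p(1−p)). The chance of ruling out the margin M is Φ[(ln M − ln r)/SE − 1.645]. The chance that the lower 95% limit exceeds 1 is Φ[ln r/SE − 1.96]. This is an unmatched approximation.

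Myotoxicity, 19 cases, margin 5:

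| r | Rules out 5 | False signal |
|---|---|---|
| 1.00 | 81% | 2.5% |
| 1.10 | 78% | 3.5% |
| 1.39 | 69% | 7.9% |
| 1.77 | 57% | 17% |
| 2.54 | 34% | 40% |

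Hepatotoxicity, 40 cases, margin 3. The protocol gives no rates by liver testing, so r is purely assumed:

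| r | Rules out 3 | False signal |
|---|---|---|
| 1.00 | 80% | 2.5% |
| 1.25 | 67% | 7.6% |
| 1.50 | 52% | 17% |
| 2.00 | 27% | 43% |

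**The case against.** The strongest reply is that the design already limits this bias. Cases come from event codes, laboratory-only cases are barred expressly to keep out chance screening findings, and myalgia needs no raised CK. This stands as a partial safeguard. It is not complete, because a test can still prompt a coded diagnosis, and myositis and rhabdomyolysis are defined by raised CK.

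Three stronger readings are tempting, and the protocol does not support them.
- *That Section 7.9 declares the bias absent.* It says similar, and it concedes that bias may differ between databases.
- *That LCZ696 users are tested more.* The label text speaks of caution, not monitoring, and no testing rates by exposure are given.
- *That the OR would be inflated to 1.39–2.54.* That range uses one of two strata from one study, neither described as a heart failure population. Monitored and unmonitored patients were different cohorts, and symptoms may have prompted the testing. The 20% figure is for CPRD patients, not for LCZ696 non-users.

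A testing covariate or sensitivity analysis may also appear in the SAP, which was not available, so its absence alone would not be a finding. But Sections 7.3.3.2 and 7.3.3.3 leave to the SAP the codes and algorithms for the listed covariates, not the list itself, and the faulty reasoning in 7.9 stands whatever the SAP adds.

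On direction, extra testing of LCZ696 users raises the OR, so it would not give false reassurance, and even 2.54 lies below the myotoxicity margin of 5. The cost is lost power and false signals. Finally, the laboratory-confirmed analysis can select further on testing, since only tested patients can be confirmed; set beside the any-case analysis, it may still be informative.

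**Conclusion.** The reasoning in Section 7.9 is wrong and should be corrected: it tests similarity between the wrong groups. Detection that differs by LCZ696 use remains possible for myotoxicity and hepatotoxicity, and following the protocol as written would leave it unexamined. Acute pancreatitis presents acutely and should be less affected.

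The size cannot be determined from the protocol. For myotoxicity, with 20% of non-users and an assumed 40–100% of LCZ696 users tested, it runs from negligible (1.02–1.06, or about 1.03–1.10) to material (1.39–2.54), depending on which cited rates apply and how much of the outcome responds to testing. For hepatotoxicity only assumed ratios can be shown.

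This is a correctable weakness in reasoning and in the checks planned. It is not evidence that the estimate will be biased by any particular amount.

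**What to change.** 1. In Section 7.9, replace the sentence with a statement that detection may differ by LCZ696 use and could raise the OR, and point to items 2 and 3.
2. Report the frequency of CK and ALT/ALP tests before the index date by LCZ696 use among controls, leaving out the last 30 days so that tests prompted by an event are not counted. This shows whether testing differs at all.
3. In Section 7.7.2.5, add a sensitivity analysis for myotoxicity and hepatotoxicity that adjusts for or stratifies by prior testing, preferably counted before LCZ696 initiation where possible. Show it beside the unadjusted result; it should not replace the primary model. Where numbers allow, add one limited to severe or hospitalised events.
4. Reconcile Section 7.3.2, where laboratory values in general only verify, with Section 7.9, where they are needed for case finding.

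**Cost.** Some wording and one derived variable for each of the two outcomes, from laboratory data that Tables 7-2 and 7-3 list for all five databases.

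**Downsides.** Tests after LCZ696 initiation may reflect true early toxicity, so adjusting for them could remove part of a real effect; hence the secondary role and the earlier window. Laboratory completeness varies by database. The severe-event analysis may be sparse: at the 0.1–2 per 10,000 PYs cited for rhabdomyolysis and the 21,000–83,000 PYs in Section 7.5, about 0.2 to 17 cases would be expected (0.00001 × 21,000 = 0.21; 0.0002 × 83,000 = 16.6).

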7.5 Study size/power calculation

The sample size is calculated following a non-inferiority approach (Wang and Chow 2007), with the intent to demonstrate that the increased risk due to LCZ696 exposure is less than 3-fold for hepatotoxicity and less than 5-fold for myotoxicity or acute pancreatitis.

Forty cases with hepatotoxicity will allow ruling out a 3-fold increased risk with a one-sided test (80% power, 5% type I error), assuming a conservative case:control ratio of 1:4 and conservatively, that 20% of the statin-exposed HF patients concomitantly use LCZ696 in the control group (Table 7-6).

Assuming an incidence rate of acute hepatic events in statin-treated HF patients of 6.1 and 12.9/10,000 PYs (Cziraky et al 2006), the underlying study base is expected to be comprised of at least about 66,000 and 31,000 patient-years (PYs), respectively.

A total of 19 cases with a myotoxic event will allow ruling out a 5-fold increased risk (Table 7-6). Assuming IR of myopathy in statin-treated HF patients between 2.3 and 9/10,000 PYs (Macedo et al 2014), the underlying study base should comprise of at least about 83,000 and 21,000 PYs, respectively.

The underlying study base should comprise of at least about 38,000 PYs in order to observe 19 cases of acute pancreatitis assuming an IR of statin-associated acute pancreatitis of 5/10,000 PYs (Kuoppala et al 2015).

Table 7-6 Sample size scenarios for a one-sided non-inferiority test (80% power, 5% type 1 error)

[figure not shown]
Risk to be ruled out	No of cases needed	
	with 10% LCZ696 use	with 20% LCZ696 use
5	33	19
3	71	40

Risk to be ruled out	No of cases needed	
	with 10% LCZ696 use	with 20% LCZ696 use
2	179	100

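### Section 7.9 wrongly argues that outcome misclassification is alike in cases and controls; where cases are not validated, false positives can make a 3- or 5-fold risk too easy to rule out

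*Protocol*

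**What the plan says.** Section 7.9 accepts that endpoints may be misclassified, and that the extent may vary with the validation and laboratory data each database holds. It then reasons that sampling and analysing within one database means "misclassification will be similar for matched cases and controls in the same database", and concludes: "Bias due to misclassification of the outcomes may just differ between the databases". It gives no direction for this bias. For LCZ696 prescriptions missing from the record, by contrast, the same section says the effect would be attenuated and plans a sensitivity analysis.

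The aim in section 7.5 is to show that any increase in risk is "less than 3-fold for hepatotoxicity and less than 5-fold for myotoxicity or acute pancreatitis".

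Several other sections bear on case validity:

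- **7.7.2** bases the final analysis on validated cases.
- **7.3.2.1 to 7.3.2.3** provide for validating all potential cases, but only in databases that permit it and have not validated the outcome previously.
- **7.9** ties endpoint validation to free text and lists PHARMO, HSD, CPRD and SIDIAP. Aarhus is not listed.
- **7.3.2** restricts narrative searching to PHARMO and says free text elsewhere is unhelpful or unavailable. Tables 7-2 to 7-4 show text for PHARMO only.
- **7.3.2** also says: "Laboratory values will in general only be used to verify the certainty of a diagnosis, which may be used in sensitivity analyses".
- **7.7.2.5** promises sensitivity analyses on the limitations, leaves their description to the SAP, and names only missing first prescriptions of LCZ696.

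**The concern.** In a case-control study, outcome error decides who is sampled as a case. A person wrongly coded with the event joins the case series. A true event that was missed can at most turn up among the controls, and with rates of 2.3 to 12.9 per 10,000 patient-years (7.5) hardly any controls are missed cases. The two errors therefore do not offset each other, and using one database for both groups does not make them do so.

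False-positive cases whose coding has nothing to do with LCZ696 carry roughly the exposure prevalence of the controls. If the true OR is above 1, they dilute it. In a study looking for a signal, dilution costs power. Here the conclusion of interest is that the upper limit lies below 3 or 5, so dilution makes a false reassurance more likely. A reader who accepts the argument in 7.9 would not look for this.

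**Working it through.** **Reproducing the protocol's own figure.** Inputs from 7.5 and Table 7-6: one-sided 5%, 80% power, 1:4 matching, and "20% of the statin-exposed HF patients concomitantly use LCZ696 in the control group". With a true OR of 1,

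n cases = (1.645 + 0.842)² × [1/(0.20 × 0.80)] × (1 + 1/4) / ln(margin)²

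This gives 40.02 for margin 3 and 18.65 for margin 5, against the stated 40 and 19. The 10% column also reproduces (71.15 and 33.15, against 71 and 33). The formula treats every case as a true case.

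**Adding false-positive cases.** PPV is not in the protocol, so a range is assumed. False positives are given the controls' exposure, p0 = 0.20.

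- Exposure among true cases: p1 = OR × p0 / [1 + p0(OR − 1)] = 0.4286 for OR 3 and 0.5556 for OR 5.
- Exposure among recorded cases: p = PPV × p1 + (1 − PPV) × p0.
- Observed OR = [p/(1 − p)] / 0.25.
- SE = √{1/[n p(1 − p)] + 1/[4n p0(1 − p0)]}.
- False rule-out rate = Φ{[ln(margin) − ln(observed OR)]/SE − 1.645}.

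Example at PPV 0.8, true OR 3, 40 cases:

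- p = 0.8 × 0.4286 + 0.2 × 0.20 = 0.3829, so the observed OR is 2.48.
- SE = √(0.1058 + 0.0391) = 0.381.
- Rate = Φ(0.190/0.381 − 1.645) = 12.6%.

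| PPV (assumed) | True OR 3, 40 cases: observed OR | False rule-out | True OR 5, 19 cases: observed OR | False rule-out |
|---|---|---|---|---|
| 1.0 | 3.00 | 5.0% | 5.00 | 5.0% |
| 0.9 | 2.73 | 8.1% | 4.33 | 8.4% |
| 0.8 | 2.48 | 12.6% | 3.76 | 13.2% |
| 0.7 | 2.25 | 18.5% | 3.26 | 19.6% |
| 0.6 | 2.03 | 25.9% | 2.82 | 27.5% |

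An unmatched simulation (200,000 runs per cell) agrees within about 1.5 percentage points, for example 11.5% and 24.4% at PPV 0.8 and 0.6 for OR 3. With 10% LCZ696 use and 71 cases, the rates at PPV 0.9, 0.8 and 0.6 are 8.0%, 12.2% and 25.1%.

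**Missed events among controls.** If 1% of controls were missed cases, a true OR of 3 would appear as 2.96; at 0.1% it stays at 3.00.

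**How few false codes matter.** At full sensitivity, 2 false codes per 10,000 patient-years give PPV 6.1/8.1 = 0.75 at the lower hepatic rate in 7.5 and 2.3/4.3 = 0.53 at the lower myopathy rate.

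**Allowing for planned validation.** Suppose only Aarhus is unvalidated, with cases in proportion to the populations in Table 7-5 (1.8 of 1.2 + 5.7 + 1.8 + 1.5 + 5.1 = 15.3 million), PPV 0.6 in Aarhus and 1 elsewhere:

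- Overall PPV = 1 − 0.4 × 1.8/15.3 = 0.953.
- p = 0.418, so a true OR of 3 appears as 2.87.
- SE = 0.377, and the false rule-out rate is Φ(0.117 − 1.645) = 6.3%.

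**The case against.** A reader might infer that the protocol dismisses outcome misclassification as harmless. It does not: the same paragraph opens by admitting the problem and closes by conceding bias that may vary by database. It also cites earlier validation work showing reliable coding.

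A reader might also take the larger error rates in the table as what this study would suffer. The documents do not support that either. Section 7.7.2 makes validated cases the basis of the final analysis, so PPVs of 0.6 to 0.8 describe unvalidated codes. If validation reaches every database but Aarhus, the inflation is about one percentage point. Section 7.7.2.5 already promises sensitivity analyses on the limitations, with detail properly left to the SAP.

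Nor do the broad Annex 3 terms prove false positives. They are suggestions for mapping, database-specific algorithms are to follow, and myalgia without raised CK is a defined part of the myotoxicity endpoint.

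Finally, the direction is conditional. The SmPC's advice of caution with co-administration could lead to closer testing or coding of co-users, which would push the OR upward. At a true OR of 1, non-differential false positives leave the OR at 1, so the stated power is unaffected.

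All of this stands, and it narrows the point. It does not rescue the argument in 7.9, and it leaves open the databases where cases are not individually validated. How many those are is unclear, because 7.9 relies on free text in four databases while 7.3.2 and Tables 7-2 to 7-4 confine text to PHARMO. The latter concern case finding rather than validation, so the statements may be compatible, but the protocol does not say so.

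**Conclusion.** The sentence in 7.9 is wrong for a case-control design, and the section omits the direction that matters for a rule-out. The harm is to type I error and depends on how much of the case series stays unvalidated. For a 3-fold margin with 40 cases, it ranges from about 6% (Aarhus alone unvalidated, PPV 0.6) to about 8-26% (nothing validated, PPV 0.9 to 0.6), against a nominal 5%.

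These figures assume a true OR at the margin, false positives independent of LCZ696, the illustrative PPVs, and an unmatched, unadjusted calculation like the one behind Table 7-6. They use the one-sided 5% test of 7.5. If the rule-out were read from the 95% interval in 7.7.2.3, the starting rate would be 2.5% and the percentages lower, with the same direction. The point deserves correction, but it does not show that the planned final analysis is invalid.

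**What to change.** 1. **Section 7.9:** replace the sentence. State that false positives occur only among cases; that, if unrelated to LCZ696 and the true OR exceeds 1, they pull the OR and its upper limit toward 1 and so favour ruling out a risk; and that differential testing or coding of co-users could reverse this.
2. **Sections 7.3.2 and 7.7.2.5:** turn the optional laboratory-confirmed analysis into a commitment to analyse validated or laboratory-confirmed cases only. Keep myalgia under its own validation, since by definition CK cannot confirm it.
3. **Section 7.7.2.5:** add a quantitative bias analysis only for databases or cases not individually validated, using the PPV from earlier validation or, failing that, a stated range. Within each database, corrected case exposure is [p − (1 − PPV) × p0]/PPV. Do not apply it to series from which false positives have already been removed, as that would correct twice. Report the corrected upper limit beside the main one; it need not become a new condition for claiming a rule-out.
4. **Sections 7.3.2 and 7.9 and Tables 7-2 to 7-4:** reconcile which databases have free text and for what purpose, and state how Aarhus cases are to be validated, if at all.

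The cost is some wording and a short calculation. The corrected limit will be less favourable and wider. As a guide, keeping the test valid at PPV 0.7 throughout would take about 73 cases instead of 40 (margin 3) and about 35 instead of 19 (margin 5).
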